**The effect of mobile application Euglyca on glycemic control of Children and Adolescents with Diabetes Mellitus Type 1**

**Thessaloniki, Greece 12/30/2016**

## Protocol

Children and adolescents with T1DM who visited consecutively our clinic were asked to participate in the study provided they owned an Android smartphone and were familiar with its use. Patients were included after one of their parents or their legal guardian signed an informed consent. Inclusion criteria were: 1. Treatment with multiple daily injections (MDI) or continuous subcutaneous insulin infusion (CSII); 2. satisfactory knowledge of the concept of carbohydrates and lipids counting acquired following previous training by the physicians and nutritionist of the department at initial diagnosis and thereafter during follow-up visits. Exclusion criteria were: 1. Use of another medical application for diabetes in the previous 3 months; 2. lack of capacity of reading greek. Eighty patients were finally eligible to participate in the study. 80 patients met the inclusion criteria and agreed to participate in the study. Subsequently they were randomized to two equally numbered groups by drawing one of two nontransparent envelopes which contained one ticket inscribed with either a E (for Euglyca group) or a C (for Control group). To ensure equal allocation rates within the 2 groups, block randomization was employed.

At the initial visit, patients randomized to the E group were advised to download the Euglyca application on their smartphones and they were asked to use the application for the calculation of the bolus insulin dose. Patients randomized to the C group were advised to calculate bolus insulin dose, the way they used to do. Patients repeated their visit to the endocrine pediatric clinic at 3, 6 and 12 months, the latter set as the terminal time-point of this study following the initial visit. At all 4 visits, anthropometrics (weight, height, BMI), blood pressure measurement and heart rate were noted down, while a peripheral blood sample was drawn from all patients in the morning of each visit after an overnight fast for measurement of glycemia and glycosylated hemoglobin (HbA1c) levels. Glucose measurements between 70 and 180 mg/dl were categorized as normoglycemia; any glucose measurement below 70mg/dl was categorized as hypoglycemia; glucose measurements at two hours postprandial measurement found above 180mg/dl were categorized as hyperglycemia. At baseline (first visit), at 6 months (third visit) and at terminal time-point (12 months) all patients filled the World Health Organization-Standard DTSQ. Patients' logbooks and readings from their glucose meters were reviewed by the physicians and nutritionist of the department at each of the four visits and the percentage of normoglycemic, hypoglycemic and hyperglycemic episodes during the preceding trimester was calculated for each patient.

The change of HbA1c values from baseline to the terminal time-point for each group was set as primary outcome, while the percentage of normoglycemic, hypoglycemic and hyperglycemic events over the total number of glucose measurements during the preceding trimester of each visit was set as secondary outcome.

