## Statistics

Sample size was determined by estimating the change in HbA1c values (primary outcome) based on previous studies (7, 8), assuming 0.5% reduction in HbA1c in the intervention group with 80% power and 5% significance level. Power calculation resulted in 14 patients per group, while the target of the study had been set at recruitment of 80 patients altogether. Results are reported as mean  $\pm$  standard deviation (SD) for quantitative variables. The absolute difference in a quantitative variable between two different time points was defined as  $\Delta$ . All quantitative variables (HbA1c;  $\Delta$ HbA1c; percentages of normoglycemic, hypoglycemic and hyperglycemic events over a total number of glucose measurements; DTSQ's scores) were normally distributed and they were compared between the two studied groups of patients at the different time-points by employing General Linear Models ANOVA and Bonferroni post-hoc test. Repeated measures ANOVA involved one factor between patients (factor "Group" with two levels) and one factor for the repeated measures within patients (factor "time" with 4 or 3 levels depending on the compared variable). Qualitative variables (gender and type of therapy) were compared by employing  $\chi^2$  (chi square) test after having computed absolute and relative frequencies (percentages %), Statistical significance was set at  $P<0,05$ . An intention to treat analysis was followed. IBM SPSS V23 Chicago, USA software was used for the statistical analysis.

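### Time since diagnosis is neither an entry criterion, a stratification factor nor a model term, so recently diagnosed children can add variance to the 12-month HbA1c change and lower power

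*Combined protocol and SAP*

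**What the plan says.** The Protocol section recruits consecutive clinic patients who own an Android smartphone and have a parent's or guardian's consent. It lists two inclusion criteria: treatment by multiple daily injections or pump, and satisfactory knowledge of carbohydrate and lipid counting, "acquired following previous training by the physicians and nutritionist of the department at initial diagnosis and thereafter during follow-up visits". It lists two exclusion criteria: "Use of another medical application for diabetes in the previous 3 months" and "lack of capacity of reading greek". None of these mentions duration of diabetes or remission.

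The 80 patients were "randomized to two equally numbered groups". On method, the section says: "To ensure equal allocation rates within the 2 groups, block randomization was employed". It names no stratification factor.

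On the outcome it says: "The change of HbA1c values from baseline to the terminal time-point for each group was set as primary outcome". The terminal time-point is 12 months.

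The Statistics section sizes the trial "assuming 0.5% reduction in HbA1c in the intervention group", with 80% power at the 5% level. It arrives at 14 per group, against a recruitment target of 80 in total. No SD is given. The repeated-measures ANOVA has a group factor and a time factor. The qualitative variables compared are gender and therapy type, and duration of diabetes is in neither the qualitative nor the quantitative list.

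**The concern.** A child who has had training at diagnosis and at a few later visits can meet every criterion. In such a child HbA1c may still be falling because insulin was started, or may later rise as a partial remission ends. Either change would lie inside the baseline-to-12-month window and would not depend on how boluses are calculated.

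The plan has no step that handles this. Entry does not limit it, allocation does not balance it, the model does not remove it, and the listed comparisons would not show an imbalance. The natural change therefore goes into the error term of the primary comparison. At stake is the power to detect a 0.5-point effect. If the outcome is read as the change within each group, the natural course also goes straight into the reported figure.

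**Working it through.** **Inputs from the documents.** Effect 0.5 HbA1c points; 5% significance (taken as two-sided, since sidedness is not stated); 80% power; 14 per group calculated; 80 patients in two equal groups, so n = 40 per arm if all are analysed.

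**Inputs assumed, because the documents give none.** SD of 12-month change in established patients, SD0; share recently diagnosed, f; mean natural fall in those children, m, with SD 1.

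**Step 1: the plan's own figure.** The 14 per group cannot be derived forward without an SD, so I solved for the SD that returns it. With n = 2(1.96 + 0.84)²·SD²/0.5², SD = 0.46 gives 2 × 7.85 × 0.2116 / 0.25 = 13.3, rounded up to 14. The two-sided range that returns 14 is 0.456–0.472 by the normal approximation and 0.437–0.454 by the t-test. One-sided or paired calculations give values up to about 0.62. I used SD0 = 0.46 as the implied value. I used 0.8 as a less favourable value, because 40 per arm holds 80% power only up to a total SD of about 0.79.

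**Step 2: spread with a mixture of patients.** Variance of change = (1 − f)·SD0² + f·1² + f(1 − f)·m².

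- SD0 = 0.8, f = 10%, m = 3: 0.9 × 0.64 + 0.10 + 0.09 × 9 = 1.486, so SD = 1.22.
- SD0 = 0.46, f = 10%, m = 2: 0.9 × 0.2116 + 0.10 + 0.09 × 4 = 0.650, so SD = 0.81.

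**Step 3: power** of the two-sample t-test on 12-month change (noncentral t, 40 per arm, effect 0.5).

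| SD0 | Natural fall m | f = 0 | 5% | 10% | 15% |
|---|---|---|---|---|---|
| 0.46 | 1 | 99.8% | 98% | 95% | 90% |
| 0.46 | 2 | 99.8% | 91% | 78% | 67% |
| 0.46 | 3 | 99.8% | 76% | 56% | 44% |
| 0.8 | 1 | 79% | 75% | 71% | 68% |
| 0.8 | 2 | 79% | 67% | 58% | 52% |
| 0.8 | 3 | 79% | 56% | 44% | 37% |

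A rise at the end of remission would add spread in the same way, since m enters as its square.

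**Step 4: bias.** In simulations of 20,000 trials per scenario (shares of 10–20%, falls of 2–3 points), type I error was 4.7–5.2% and the mean estimated difference was 0.50. The between-arm contrast is not biased.

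**Step 5: within-group reading.** The mean change in each arm moves by f × m: 10% × 2 = 0.2, 15% × 3 = 0.45, 20% × 3 = 0.6. The last exceeds the assumed effect of 0.5.

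**Step 6: effect of adjustment.** Simulating the scenarios of Step 3 with a yes/no recent-diagnosis term gives power of about 75–78% at SD0 = 0.8 and 97–99% at SD0 = 0.46, close to the figures with no recent patients. Baseline HbA1c alone recovers only part of the loss, by an amount that depends on assumed baseline distributions.

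**The case against.** Three objections carry weight.

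First, entry within weeks of diagnosis is unlikely. At every visit, including the first, logbooks and meter readings for the preceding trimester are reviewed and percentages calculated for each patient. The training text speaks of follow-up visits in the plural, and controls are told to keep their existing way of calculating boluses. This stands, and it makes the 3-point fall an extreme case. It is still not a duration rule: a child several months after diagnosis remains eligible.

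Second, the share, the natural fall and the SD are all assumed. At the SD implied by the plan's own calculation, 80 patients absorb a good deal: power stays at 90% or more with a 1-point fall, and is 91% with 5% recent and a 2-point fall. This also stands, so the point has to be given as a range.

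Third, a reader might infer that natural course could swamp the 0.5-point effect, or create a false difference between arms. The documents do not support that. Allocation is randomised, both arms share the natural course in expectation, and the test keeps its 5% error rate. Chance imbalance is possible: with 8 such children, a split of 6 versus 2 at a 3-point fall shifts the difference by (6/40 − 2/40) × 3 = 0.3, and a split at least that uneven occurs about 26% of the time. But that is the same variance already counted in the standard error, not a further harm.

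**Conclusion.** The omission is certain from the text; its size is not. Time since diagnosis is uncontrolled at entry, allocation and analysis, so recently diagnosed children can add variance to the primary outcome. The between-group comparison remains valid, and the cost is precision.

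On the assumptions shown, the cost runs from negligible (98% power at SD 0.46, 5% recent, 1-point fall) to serious (37% at SD 0.8, 15% recent, 3-point fall). At SD 0.46 with a 10% share, power drops just below the 80% target with a 2-point fall (78%). At SD 0.8 there is no margin to begin with (79%).

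The natural course enters the estimate directly only if the primary outcome is read as a change within each group, a reading that its wording allows. This is a moderate point, worth acting on because the remedy is cheap.

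**What to change.** State the primary comparison as the between-group difference in 12-month HbA1c change. Take the date of diagnosis from the clinic file, and add recent diagnosis (for example under 12 months before baseline, yes/no) and baseline HbA1c to that model. Tabulate time since diagnosis by group, and report a sensitivity analysis without the recently diagnosed patients. The 12-month cut-off is an example, not derived from the documents; set it before group results are seen, or label the analysis post hoc. State the SD behind the 14 per group, so that readers can judge the margin at 80 patients.

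If enrolment is still open, a minimum time since diagnosis is an alternative. The text reports the 80 patients as already randomised, so the analysis route is the more usable one.

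Cost: one extra data item, the model terms and one sensitivity analysis. Exclusion would instead shrink the consecutive pool and limit the conclusion to established type 1 diabetes.

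### Type of therapy (MDI or CSII) is recorded but used neither in the stated blocking nor in the HbA1c model, so chance imbalance goes unadjusted and a difference in effect by regimen would not be seen

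*Combined protocol and SAP*

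**What the plan says.** Inclusion criterion 1 in the Protocol section is "Treatment with multiple daily injections (MDI) or continuous subcutaneous insulin infusion (CSII"), so both regimens form one population. Patients in the Euglyca arm receive one instruction whatever their regimen: "they were asked to use the application for the calculation of the bolus insulin dose". For controls the text is "Patients randomized to the C group were advised to calculate bolus insulin dose, the way they used to do". It does not say what that earlier method was, whether it differed between regimens, or whether it is recorded. The only exclusion touching other dosing aids is "Use of another medical application for diabetes in the previous 3 months".

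On allocation, patients are "randomized to two equally numbered groups", and the stated purpose of blocking is equal numbers: "To ensure equal allocation rates within the 2 groups, block randomization was employed". No stratification by therapy is mentioned.

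In the Statistics section, therapy type appears once: "Qualitative variables (gender and type of therapy) were compared by employing" a chi-square test. The outcome model has a single between-patient factor, group: "Repeated measures ANOVA involved one factor between patients (factor 'Group' with two levels"). No covariate, interaction or subgroup analysis by therapy is stated.

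**The concern.** The app does one job, bolus calculation, so the control arm's method of calculating the bolus is the comparator. If that method differs between MDI and CSII users, the size of the app's effect may differ too, and the pooled estimate is then an average weighted by the clinic's mix of regimens. The plan collects the variable that could reveal this and stops at a comparison of frequencies.

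Two things are at stake. First, with no stratified blocks and no therapy term in the model, an accidental imbalance in regimen carries into the primary ΔHbA1c comparison without adjustment; the chi-square test may display it but cannot correct for it. Second, if the app helps one regimen more than the other, the pooled figure understates the effect in one and overstates it in the other, and nothing planned would show that. A weak pooled result could be read as the app failing everywhere, or a strong one extended to patients who gained little.

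**Working it through.** **Inputs from the documents.** Effect 0.5% HbA1c, 80% power, 5% significance level, 14 per group calculated, 80 patients in two equal groups (40 per arm).

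**Inputs assumed.** The documents give no CSII share, no SD and no effect by regimen. I use CSII shares of 20 / 30 / 50% and SDs of 0.47, 0.8 and 1.0.

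**1. The plan's own figure.** With the two-sided two-group normal formula, n = 2(1.96 + 0.84)² SD² / 0.5². Setting n = 14 and solving gives SD = 0.5 × √7 / 2.80 ≈ 0.47; an SD of 0.456 to 0.472 rounds up to 14. Other readings of the calculation give other values: 0.437 to 0.454 with the t distribution, 0.513 to 0.532 one-sided, and about 0.67 for a one-sample change. The figure of 14 is therefore attainable but cannot be confirmed, and 0.47 is an inferred value.

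**2. Chance imbalance.** Take 80 patients, 40 per arm and K on CSII. The number X of CSII users in one arm is hypergeometric, and the arms differ by |2X − K| / 40. The block size is not stated, so this treats allocation as a random split into two equal halves.

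| CSII share (K) | P(difference ≥ 15 points) | P(difference ≥ 20 points) |
|---|---|---|
| 20% (16) | 16% | 5% |
| 30% (24) | 22% | 9% |
| 50% (40) | 26% | 12% |

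The shift this causes in the E-minus-C estimate is the imbalance times the difference between regimens in mean ΔHbA1c. If that difference were 0.5% (assumed), a 15-point imbalance would move the estimate by 0.15 × 0.5 = 0.075%.

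**3. Dilution in the extreme case.** Suppose a 0.5% effect in MDI users and none in CSII users. The pooled effect is 0.5 × (1 − CSII share): 0.5 × 0.8 = 0.40, 0.5 × 0.7 = 0.35 and 0.5 × 0.5 = 0.25. Power is from the noncentral t, two-sided 5%, 40 per arm:

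| SD | No dilution | 20% CSII | 30% CSII | 50% CSII |
|---|---|---|---|---|
| 0.47 | 99.7% | 96% | 91% | 65% |
| 0.8 | 79% | 60% | 49% | 28% |
| 1.0 | 60% | 42% | 34% | 20% |

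The diluted effects do not depend on the SD; the power figures depend on it heavily.

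**4. What an interaction test could show.** The standard error of the difference in effect between regimens is SD × √(2/n_MDI + 2/n_CSII), with n the number per arm in each regimen. At 20% CSII and SD 0.8 this is 0.8 × √(2/32 + 2/8) = 0.447, so a true difference of 0.5 has about 20% power. At 50% CSII and SD 0.8, power is 29%. At SD 0.47 the two figures are 48% and 66%.

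**The case against.** The strongest reply is that usual practice is a legitimate comparator. For consecutive patients at one clinic, the average effect of adding the app to whatever they already do is a coherent question, and randomisation answers it without bias. The test's error rate already allows for chance imbalance, and taking change from baseline removes stable differences in HbA1c level between regimens. All of that stands. A therapy main effect in the model would not undo dilution either, and the interaction test is weak.

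A reader might go further and infer that CSII users already have an automated bolus calculator in the pump, so that for them the trial sets one calculator against another. The documents do not support this. They describe neither the pumps nor how patients on either regimen calculated their boluses, and they require satisfactory knowledge of carbohydrate and lipid counting from all patients. Nor do they say that the app exclusion was meant to secure an unaided control arm; it may simply avoid contamination by competing apps. A zero effect in CSII users is likewise only a bounding assumption.

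A reader might also quote a fall in power from 79% to 28% as the expected loss. That needs SD 0.8, half the patients on CSII and no effect in any of them. At the SD implied by 14 per group, power stays above 90% at 20 to 30% CSII even in the zero-effect case.

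The reply does not explain why a prognostic or effect-modifying variable that is already collected should be left out of both the blocking and the model.

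**Conclusion.** The concern holds as a gap in efficiency and interpretation. The primary test is not biased, and the documents do not show that the app faces two different comparators; that is possible if usual bolus calculation differs by regimen.

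On size, a 15-point imbalance in therapy type is fairly common (about one allocation in six to one in four over the assumed shares), but its effect on the estimate is modest unless mean change differs strongly by regimen. Dilution could halve the pooled effect in the most extreme case considered. Its cost in power runs from slight to severe depending on an SD that the plan does not state. The CSII shares, the zero effect and the SDs of 0.8 and 1.0 are assumptions; 0.47 is inferred from one reading of the sample size calculation. The change is worth making because it costs almost nothing.

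**What to change.** Add therapy type (MDI or CSII) as a between-patient factor in the primary ΔHbA1c model. If allocation has not yet been done, keep separate envelope blocks for MDI and CSII; the Protocol section is written in the past tense, so this may no longer be possible, whereas the model factor still is.

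Report the E-minus-C difference with its confidence interval separately for MDI and CSII, together with the group-by-therapy term. Label these exploratory and state that the interaction has low power, so that a non-significant term is not taken as evidence of equal effects. Describing and recording each patient's usual way of calculating boluses would help readers interpret the comparator.

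The cost is two envelope sets instead of one, one extra factor in the existing SPSS model and one baseline item. On the downside, two strata can leave the arms unequal by a patient or so, and the by-therapy estimates will be imprecise. No treatment rule changes.

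### Hyperglycemia counts only two-hour postprandial readings above 180 mg/dl but is divided by all readings, so other high readings have no category and the percentage depends on when patients test

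*Combined protocol and SAP*

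**What the plan says.** The Protocol section sets two of the three glucose categories without any limit on time of day: "Glucose measurements between 70 and 180 mg/dl were categorized as normoglycemia; any glucose measurement below 70mg/dl was categorized as hypoglycemia". The third carries a timing condition: "glucose measurements at two hours postprandial measurement found above 180mg/dl were categorized as hyperglycemia".

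The secondary outcome is then defined as "the percentage of normoglycemic, hypoglycemic and hyperglycemic events over the total number of glucose measurements" in the trimester before each visit. The Statistics section repeats that denominator when it lists the variables to be compared: "percentages of normoglycemic, hypoglycemic and hyperglycemic events over a total number of glucose measurements".

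The readings come from patients' logbooks and glucose meters. The documents state no testing schedule, no number of postprandial tests, no denominator restricted to postprandial readings, and no plan to report when patients tested.

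**The concern.** The numerator and denominator of the hyperglycemia percentage refer to different sets of readings. A fasting, pre-meal, bedtime or night reading of, say, 250 mg/dl counts in the denominator, is neither normoglycemic nor hypoglycemic, and cannot be hyperglycemic under the rule. The three percentages therefore need not add to 100%, and the shortfall is made up entirely of high readings.

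Two things are at stake. First, the hyperglycemia percentage understates the frequency of high readings whenever any fall outside the two-hour window, even if both groups test identically. Second, the percentage mixes testing times with glycemia. Only the Euglyca group is asked to use an app for bolus calculation, so the timing of tests could change in one group and not in the other. Fewer postprandial tests in that group would favor the app, and more would count against it. With no planned report of testing times, a reader could not tell such a shift from a real change in glycemia.

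**Working it through.** The documents give no figure for this outcome to reproduce. Their only calculated figure, 14 patients per group, concerns HbA1c and does not enter here.

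**Step 1: do the categories cover every reading?** Taking the 70 to 180 range as inclusive:

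| Reading | Two hours after a meal | Any other time |
|---|---|---|
| Below 70 | Hypoglycemia | Hypoglycemia |
| 70 to 180 | Normoglycemia | Normoglycemia |
| Above 180 | Hyperglycemia | No category |

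One cell is empty, and nothing elsewhere in the documents fills it.

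**Step 2: what the reported percentage measures.** Let s be the postprandial share of all readings, p the proportion of postprandial readings above 180, and q the proportion of other readings above 180. Then:

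- reported hyperglycemia = s × p
- readings in no category = (1 − s) × q
- all readings above 180 = s × p + (1 − s) × q = 100% − normoglycemia − hypoglycemia

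For fixed p, the reported figure is exactly proportional to s.

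**Step 3: illustration.** The documents supply none of s, p or q, so all values are assumptions. With p = 50% and q = 35%:

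| s | Reported (s × p) | No category | All above 180 | Sum of the plan's three percentages |
|---|---|---|---|---|
| 20% | 10.0% | 0.80 × 35 = 28.0% | 38.0% | 72.0% |
| 30% | 15.0% | 0.70 × 35 = 24.5% | 39.5% | 75.5% |
| 40% | 20.0% | 0.60 × 35 = 21.0% | 41.0% | 79.0% |

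A 10-point rise in s moves the reported figure by 10 × 0.50 = 5.0 points and the all-readings figure by 10 × (0.50 − 0.35) = 1.5 points.

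The mechanism is plainest when p = q = 40%, so that glycemia is the same at all times of day. Shares of 20%, 40% and 60% then give reported hyperglycemia of 8%, 16% and 24%, while all readings above 180 stay at 40%.

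**Step 4: range.** For p from 40% to 60% and q from 25% to 45%, a 10-point rise in s changes:

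- the reported figure by 10 × p, which is 4.0 to 6.0 points
- the all-readings figure by 10 × (p − q), which is −0.5 points (0.40 − 0.45) to +3.5 points (0.60 − 0.25)

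For s from 20% to 40% and the same q, readings in no category run from 0.60 × 25 = 15.0% to 0.80 × 45 = 36.0%.

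**Step 5: can a reader recover the truth from the planned results?** The reported percentages fix two quantities, s × p and (1 − s) × q, but there are three unknowns. For example, s = 20%, p = 50%, q = 35% gives 10% reported and 38% in total. So does s = 30%, p = 33.3%, q = 40%: 0.30 × 33.3 = 10% and 0.70 × 40 = 28%, again 38% in total. Postprandial control differs clearly between the two cases, yet the published figures would be identical.

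**The case against.** The strongest points on the other side, and what stands of each:

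- **No bias is shown.** Allocation is randomized and there is a baseline visit, so the group comparison is distorted only if testing times change differently after randomization. This stands: the bias is possible, not demonstrated. The missing category does not depend on it.
- **A reader can subtract.** Normoglycemia and hypoglycemia are to be reported, so the group mean of all readings above 180 can be derived. This is true, and useful, but Step 5 shows that it does not separate testing times from glycemia. The derived figure also comes without an SD or a test.
- **Staff may have counted every reading above 180.** The rule cannot be applied unless two-hour postprandial readings are identified, and the documents do not say that meal timing is recorded. The concern is therefore about the written rule, not about what was done. If practice differed, the text still has to be corrected.
- **Episodes are not readings.** The Protocol section also says "the percentage of normoglycemic, hypoglycemic and hyperglycemic episodes during the preceding trimester was calculated for each patient". If several readings formed one episode, the subtraction would fail. However, the categories are defined on measurements and the stated denominator is measurements, so one reading counting once is the natural interpretation. It should be made explicit.
- **Redefinition makes hyperglycemia redundant.** Once it is 100% minus the other two percentages, its comparison adds no independent information. This stands and is a cost of the fix.
- **Postprandial glucose is the natural target for a bolus calculator.** It may be, but then the denominator should be postprandial readings.

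**Conclusion.** The concern holds and should be fixed. Followed as written, the rule leaves high readings outside the two-hour window unclassified and yields a hyperglycemia percentage that depends on the postprandial share of tests. This follows from the definitions and needs no assumed data. The sizes do: under the assumed ranges, 15.0% to 36.0% of readings would have no category, and a 10-point difference in postprandial share would shift reported hyperglycemia by 4.0 to 6.0 points with p and q unchanged. Whether testing times differ between groups or visits is unknown.

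The scope is one of the three components of the secondary outcome. The timing rule does not restrict the normoglycemia and hypoglycemia percentages, and HbA1c is unaffected.

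**What to change.** 1. In the outcome definition, apply the plan's own 180 mg/dl limit to all readings and state that each reading counts once. Hyperglycemia is then 100% minus normoglycemia minus hypoglycemia for each patient and visit.
2. If postprandial hyperglycemia is of interest, report it as a separate measure with two-hour postprandial readings as its denominator.
3. Where meal timing is recorded, tabulate by group and visit the number of readings per patient and the postprandial share. The all-readings percentage still varies somewhat with testing times (1.5 points in the first illustration, against 5.0), so the first change reduces the dependence without removing it.

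**Cost.** The redefinition takes one sentence, and the new figure is a subtraction from two percentages already calculated per patient, so no recount is needed. Items 2 and 3 require the meal timing of each reading, which the documents do not say is available, as well as extra tables. Hyperglycemia percentages will be higher than under the current rule wherever high readings occur outside the window, and the three percentages will be linearly dependent. The Statistics section is written in the past tense; if the data had already been examined when the definition is changed, the change should be labeled post hoc.

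### The primary comparison of 12-month HbA1c change is valid but leaves out baseline HbA1c as a covariate; adding it narrows the interval by about 5 to 13% with no new data.

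*Combined protocol and SAP*

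**What the plan says.** The Protocol section defines the primary outcome: "The change of HbA1c values from baseline to the terminal time-point for each group was set as primary outcome". The end point is 12 months: "Patients repeated their visit to the endocrine pediatric clinic at 3, 6 and 12 months, the latter set as the terminal time-point". HbA1c is available at baseline and at every later visit, because "a peripheral blood sample was drawn from all patients in the morning of each visit".

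The Statistics section again labels HbA1c change as the primary outcome when it describes the sample size. It lists HbA1c and ΔHbA1c among the quantitative variables and says "they were compared between the two studied groups of patients at the different time-points by employing General Linear Models ANOVA and Bonferroni post-hoc test". It then describes a second model: "Repeated measures ANOVA involved one factor between patients", with time as the within-patient factor. Group and time are the only factors named, and no covariate appears. In the repeated-measures model the baseline value enters as one level of time.

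On size, "Power calculation resulted in 14 patients per group" for a 0.5 percentage-point reduction at 80% power and 5% significance, with a recruitment target of 80. No SD and no correlation between visits is given.

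**The concern.** A change score subtracts the whole baseline value, which amounts to fixing the regression slope on baseline at 1. If SDs are equal at the two visits, the true slope equals the correlation between them and is below 1. Fixing it at 1 leaves avoidable noise in the estimate. It also over-corrects when the arms happen to differ at baseline: the arm that starts higher tends to show the larger fall even if the app does nothing.

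At stake are the width of the interval around the main result, some power, and how far that result depends on the luck of the baseline draw with 40 patients per arm. Bias and overall false-positive rate are not at stake.

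**Working it through.** **Inputs.** From the documents: 40 per arm (target of 80, equal groups), difference 0.5, significance 5%, power 80%, 14 per group. Assumed because the documents are silent: two-sided test, no dropout, equal SD s at baseline and 12 months, correlation ρ from 0.5 to 0.8, and s = 1.0 where an absolute SD is needed.

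**The plan's own figure.** The 14 per group cannot be reproduced without an SD, so solve for the SD that gives it, with (1.960 + 0.842)² = 7.849.
- Two-sample reading: SD = √(14 × 0.5² / (2 × 7.849)) = √(3.5/15.698) = 0.472. With the t distribution it is 0.455.
- Paired reading: SD = √(3.5/7.849) = 0.668. With the t distribution it is 0.617.

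**Precision.** Var(change) = 2s²(1−ρ). Var(adjusted) = s²(1−ρ²). The variance ratio is (1+ρ)/2, whatever the value of s. Power is from the noncentral t (78 df for change, 77 df adjusted) for a difference of 0.5, with s = 1.0.

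| ρ | SE ratio √((1+ρ)/2) | Interval narrower by | Power, change | Power, adjusted |
|---|---|---|---|---|
| 0.5 | 0.866 | 13.4% | 60% | 72% |
| 0.6 | 0.894 | 10.6% | 69% | 79% |
| 0.7 | 0.922 | 7.8% | 81% | 87% |
| 0.8 | 0.949 | 5.1% | 94% | 96% |

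The ratios are large-sample values. Estimating the slope costs about 1.3% in variance (1/76) and one degree of freedom. Simulated trials at 40 per arm give SE ratios of 0.873/0.902/0.929/0.955, so the interval is 12.7/9.8/7.1/4.5% narrower. In HbA1c points at s = 1.0, the 95% half-width goes from about 0.44/0.40/0.34/0.28 to 0.39/0.36/0.32/0.27. Allowing for the 1.3%, the gain vanishes only when (1+ρ)/2 × (1 + 1/76) reaches 1, that is, at ρ of about 0.97.

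**Power at the SD of change implied by 14 per group** (40 per arm, difference 0.5, adjusted range over ρ = 0.8 to 0.5):
- Two-sample, SD 0.455–0.472: the change test already has 99.7–99.8%; adjusted is above 99.8%.
- Paired, SD 0.668: 91.1% rises to 93.6–96.8%. Paired, SD 0.617: 94.7% rises to 96.5–98.5%.

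**Chance imbalance.** The baseline difference between arms has standard error s√(2/40) = 0.224s, so it exceeds 0.3 SD with probability 2(1 − Φ(0.3/0.224)) = 18%. Given a baseline difference b and no app effect, the expected difference in change is −(1−ρ)b. Error rates from 60,000 simulated null trials per correlation, ρ = 0.5/0.6/0.7/0.8:
- Change test, imbalance beyond 0.3 SD: 11.8/10.5/8.8/8.0%. A separate run of the same size gave 10.9/10.2/8.6/7.5%, so about 7–12% in all.
- Change test, remaining trials: 3.5/3.9/4.1/4.5%.
- Change test, all trials: about 5%. Check at ρ = 0.5: 0.18 × 11.8 + 0.82 × 3.5 = 5.0.
- Adjusted test: about 5% in both subsets.

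When E starts more than 0.3 SD higher, the mean baseline gap is about 0.40 SD. The change test then shows a mean spurious E advantage of 0.20/0.16/0.12/0.08 at s = 1.0, against roughly 0 after adjustment.

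**The case against.** The strongest reply is that nothing here is wrong: the comparison of change scores is a legitimate analysis, and preferring baseline adjustment is good practice, not correction of an error. That stands. So does the point that the larger power gains need an SD of about 1.0, which the plan does not give; at the SD implied on the two-sample reading, power has nowhere to go. The Statistics section is also in the past tense and reports that variables were normally distributed. If outcomes have been seen, adjustment can no longer be pre-specified.

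A reader might infer more than the documents support.
- *That no primary analysis is identifiable.* No sentence says outright which test decides, and Δ is defined loosely: "The absolute difference in a quantitative variable between two different time points was defined as" the symbol, without fixing the two times. But the Protocol fixes the variable and the 12-month end point, and the Statistics section repeats the primary label and compares ΔHbA1c between groups. Inflated error rates obtained by counting the 12-month level or other tests as rival primaries do not follow.
- *That success will be judged within each group.* Since "readings from their glucose meters were reviewed by the physicians and nutritionist of the department at each of the four visits", a fall common to both arms is conceivable. But the stated analysis is between groups, so the per-group wording of the outcome is weak evidence for a within-group test.
- *That a three-visit Bonferroni correction erodes the primary test.* The plan does not say that the correction covers it.
- *That the change score ignores baseline imbalance, or is biased.* It over-corrects, and over all randomisations it is unbiased with 5% error.

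**Conclusion.** The point holds as one of precision. The planned comparison is valid, but it omits a covariate that is already collected. The dependable gain is an interval about 5 to 13% narrower for correlations of 0.8 down to 0.5 with equal SDs, and slightly less once slope estimation is counted. The size of the power gain cannot be settled from the documents. It is negligible if 14 per group came from a two-sample calculation, a few points if it came from a paired one, and 2 to 12 points if the SD of HbA1c is 1.0. Protection against chance baseline differences is a second, real benefit that matters in roughly one trial in five or six of this size. The missing covariate is certain from the text; the magnitudes rest on the assumptions stated.

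**What to change.** Make the primary analysis the E-minus-C difference in 12-month HbA1c from a linear model with group as factor and baseline HbA1c as covariate, tested two-sided at 5% and reported with its 95% confidence interval. State that this one result answers the primary question. Label the Group effect, the Group × time interaction, the 3- and 6-month comparisons and the within-group changes as supportive, and confine any Bonferroni correction to them.

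If outcome data have already been seen, keep the between-group comparison of 12-month ΔHbA1c as primary and report the baseline-adjusted result beside it, labelled post hoc.

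The cost is a sentence or two and one model term. No extra patients, visits or measurements are needed.
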